## 2.4 Determination of sample size

Based upon the ICH guideline for the assessment of safety, it is planned to enroll a sufficient number of study participants to this study to have a minimum of 100 with at least 12 months continuous exposure to CZP. Assuming a dropout rate of approximately 20%, it was originally determined that 125 study participants would need to be enrolled. At the time of Protocol Amendment 5, 78 study participants had been enrolled according to the Original CZP Dose, and it was planned to enroll a further 78 study participants on the Reduced CZP Dose, so that a comparable number of study participants on the Reduced CZP Dose could be

Confidential

analyzed. Thus, the total number of study participants planned to be enrolled was increased to 156 study participants. Assuming a Screening failure rate of 25%, it was planned to screen 195 study participants in total.

Valiations thereof With Protocol Amendment 9, an additional 30 study participants were enrolled with the aim to enroll at least 5 study participants in each weight range of 10 to <20kg (22 to <44lb), 20 to <40kg (44 to <88lb), and >40kg (>88lb).

Prior to the start of study conduct, simulations using the adult population PK model in pediatric study participants with pcJIA suggested that the planned sample size of 125 study. participants would also be adequate for PK assessment purposes. Individual apparent clearance (CL/F) and volume of distribution (V/F) were simulated for a total of 125 study participants (using the same approach presented in C87079 report addendum 08 Oct 2008 performed for 190 study participants). In all age groups, the standard errors of both PK parameters, CL/F and V/F, relative to their mean were substantially <20%, with values ranging from 5.5 to 7.0% for CL/F and from 4.6 to 7.5% for V/F.

Available ECLIA-based data from all study participants were included in the final PopPK analysis as described in a separate Data Analysis Plan and reported separately for the Updated Week 24 Interim Analysis only.

#### 2.5 Study RA0138

RA0138 is an open-label study in 33 adult study participants with RA who took 400mg loading dose (Weeks 0, 2, and 4), followed by 200mg CZP Q2W. This study was conducted to generate PK and ADAb data using the same ECLIA assay as used in RA0043 to form the basis of "PK-matching" for CZP approval. For Updated Week 24 Interim Analysis, the PK and ADAb data from RA0138 was analyzed and displayed in the same manner as data from RA0043; comparisons and conclusions were made. Those details are presented in the Appendix, Section 12.1.

Generally, data will be summarized by the Original CZP Dose, Reduced CZP Dose, and Any CZP Dose groups. For PK and ADAb analyses, data will be summarized by Original CZP Dose and Reduced CZP Dose only. For the Juvenile Arthritis School Attendance and Caregiver Work Productivity Survey, data will be summarized by Any CZP Dose group only.

Following recommendations received from

, a few data summaries were organized for the Updated Week 24 Interim Analysis only, by "Complete" CZP dose groups defined below, which allowed assessment of exposure and safety for all time that study participants were receiving the specified dose regardless of dose switching:

• Complete Original CZP Dose: included all study participants who began treatment in accordance with the Original CZP Dose, as well as study participants who began treatment in accordance with the Reduced CZP Dose and then later dose escalated to the Original CZP Dose.

Only data obtained while the study participant was receiving the Original CZP Dose was included in summaries of the Complete Original CZP Dose. For study participants who began treatment with the Original CZP Dose, this included time on the Original CZP Dose prior to first change in dosage, as well as time after returning to Original CZP Dose after a previous dose reduction. For study participants who began treatment with the Reduced CZP Dose, this included only time after dose escalation to the Original CZP Dose.

Complete Reduced CZP Dose: included all study participants who began treatment in accordance with the Reduced CZP Dose, as well as study participants who began treatment in accordance with the Original CZP Dose and later dose reduced to the Reduced CZP Dose.

Only data obtained while the study participant was receiving the Reduced CZP Dose was

included in summaries of the Complete Reduced CZP Dose. For study participants who began treatment with the Reduced CZP Dose, this included time on the Reduced CZP

Selected exposure and TEAE summaries were produced on Complete Original CZP Dose and Complete Reduced CZP Dose in order to answer specific agency questions. Similarly, summaries of the proportion of PK and ADAb samples and participants that have been reanalyzed with the ECLIA assay were also produced with this treatment.

respective PK, safety and efficacy analysis sections below.

Categorical data will be presented as summary tables. A missing category will be included as applicable.

Continuous variables will be summarized with the mean, standard deviation, median, minimum, and maximum. For CZP plasma concentrations and CRP, the geometric mean and geometric coefficient of variation (CV) will be presented.

Due to shifts in visit schedules per protocol amendments that were adopted at different times for different sites and study participants, some visits/ time points had very few study participants assessed. For categorical and continuous efficacy variables presented by visit/time point, if the visit/time point for the Any CZP Dose group contains 19 or fewer study participants with non-missing data, those visits/ time points will not be displayed in the efficacy tables or plotted in figures for Reduced CZP Dose, Original CZP Dose and Any CZP Dose groups. All information will appear in the listings.

Mean, standard deviation, and median will be displayed to 1 more decimal place than collected in the case report form (CRF). Minimum and maximum values will be displayed to the same level of precision as collected in the CRF. Percentages will be calculated using the number of study participants in the relevant population or subgroup as the denominator. Presentation of percentages will be to 1 decimal place. Percentages will not be presented if the frequency count is 0.

No formal statistical hypothesis testing will be performed. Ninety-five percent confidence intervals (CIs) for the percentage of responders will be calculated using the exact binomial method.

For certain laboratory parameter results that are collected as either "<XX.X" or ">XX.X", if descriptive statistics are calculated for the parameter, the XX.X will be used in the calculation

The classification of AEs occurring on the same date as a dose change will belong to the period of the dose change.

In addition, for other subgroup analyses (e.g. Baseline age group, concomitant MTX use, etc.), data will be generally presented by the specified subgroups pooling across all weight groups (with the exception of PK analyses which are specified in the corresponding sections).

## 3.2 General study level definitions

## 3.2.1 Analysis time points

The analysis time points of interest are detailed in Table 2–2. Safety assessments will also be done at the Final Visit 12 weeks after the final dose of CZP.

For study participants who withdraw prior to the last time point for the particular analysis being conducted (ie, Week 16, Week 24, other interim analysis, Final), data recorded at the Early Discontinuation/EOT Visit will be assigned to what would have been the next scheduled visit, unless unavailable or otherwise specified, dependent on which visit schedule the study participant is following. This re-assignment should be based upon the study day (relative to the baseline visit date) and also keeping in mind the +/- 3-day window into which visits fall. These data will be included in the summaries of the assigned visit and the "Early Discontinuation/EOT" Visit if applicable. For efficacy data, the Early Discontinuation/EOT Visit will not be summarized and only the re-assigned visit will be included in the summary tables. Note that data from the Early Discontinuation Visit or EOT will be listed as "Visit X (Week Y)/ED" or "Visit X (Week Y)/EOT" where the X was the re-assigned visit number and Y was the re-assigned week number in all safety and efficacy data listings as applicable.

## 3.2.2 Relative day

Relative day of an event or assessment will be included in data listings and will be calculated as follows:

Relative day 1 is the date of first CZP administration.

Relative day of date X = date X - Date of first CZP administration+1 day if date X is on or after date of first CZP administration.

Relative day of date X = date X - Date of first CZP administration if date X is before date of first CZP administration.

Relative days before first administration of CZP will have the prefix "-".

Relative day after last dose will have the prefix "+",and will be calculated from the date of last CZP administration (date X - date of last CZP administration). Relative day will not be calculated when any part of a corresponding date is missing,and will not be included in corresponding tables and listings.

## 3.2.3 Medications

The UCB study physician will review a listing of all medications and flag those which are steroids, DMARDs, anti-TNFs, NSAIDs, Cox 2 inhibitors, analgesics, opioids, experimental medications, vaccines, etc. This flagging is then used to generate various medication tables.

## 3.2.4 Final Visit

Final visit is defined as the visit conducted 12 weeks after the last dose of study medication. Most efficacy variables state that the Final Visit data will not be included in table summaries; the data will be included in study participant data listings.

Confidential Page 26 of 252

#### 3.2.5 Week 24

Week 24 is defined as the visit labeled as Week 24 or Visit 10 in the data.

Definition of Baseline values

The Baseline value for all variables will be the last non-missing pre-treatment measurement. The last non-missing pretreatment measurement will generally be the Baseline (Week 0) visit, but could be the Screening Visit if no Baseline value was obtained or an Visit that occurs prior to first dose. For study participants or Reduced CZP Dose, Baseline is the last the initial dose on the One of the last non-missing pre-treatment measurement will generally be the Baseline (Week 0).

The change from Baseline will be calculated as the difference between the post-Baseline value and last non-missing pre-treatment measurement. Change from Baseline will only be calculated if a valid Baseline value is available.

#### 3.4 **Protocol deviations**

Important protocol deviations will be pre-defined and data cleaning meetings will be held on an ongoing basis to review the important protocol deviations. At these data cleaning meetings, protocol deviations from the Clinical Trial Management System (CTMS) as well as those generated programmatically will be reviewed by the study team in order to flag those that are important.

In addition, protocol deviations related to the impact of the global pandemic of coronavirus disease 2019 (COVID-19) will be documented.

Study participants, if taking CZP Q2W, should be dosed 9 to 19 days from the previous dosing; if taking CZP Q4W, study participants should be dosed 23 to 33 days from the previous dosing. Study participants who are taking CZP Q2W, if they have instances where they take their study medication > 42 days from the last dosing, or for those who are taking CZP Q4W, if they have instances where they take their study medication > 84 days from the last dosing, these instances will be flagged as important protocol deviations. For study participants not in derived CRM and taking CZP Q2W, gaps less than 9 days or >19 to 42 days will be considered as protocol deviations. For study participants not in derived CRM and taking CZP Q4W, gaps less than 23 days or >33 to 84 days will be considered as protocol deviations.

## 3.5 🗘 **Exclusion of PK data points**

Exclusion of specific PK data points will be done for that CZP plasma concentration data presented in the subset of tables and figures where geometric means are calculated and displayed. These exclusions will not occur in the CZP plasma concentration data presented in spaghetti plots or individual profile figures. The reasons why CZP plasma concentration data points may be excluded are the following:

Confidential Page 27 of 252

- Study participant taking an incorrect treatment or dose,
- Study participant's discontinuation of CZP,
- Study participant being in derived CRM (and not taking CZP),
- Study participant having deviations where CZP dosings occur outside the scheduled CZP dosing window, and
- Study participant is procedurally non-compliant, in not having plasma concentration samples taken at the appropriate time points.

CZP plasma concentration data that is excluded due to the above reasons will be flagged on the analysis PK dataset. The flagging will allow the data to be excluded from geometric mean calculations which could be more affected by instances of treatment and procedure non-compliance.

## 3.5.1.1 Rules for exclusions of specific PK samples

The PK sample results taken at a specific visit will be excluded from analysis for the following reasons:

- If the study participant's CZP plasma concentration sample was taken at a visit where the prior 2 consecutive CZP doses were missed, then the study participant's CZP plasma concentration sample is excluded,
  - For study participants returning to CZP dosing, a study participant's CZP plasma concentration result will be included in summaries if the prior 3 consecutive CZP doses are present.
- If in the 168 days prior to the study participant's CZP plasma concentration sample, there were >3 CZP doses missed, then that study participant's CZP plasma concentration sample is excluded,
  - For study participants returning to CZP dosing, a study participant's CZP plasma concentration result will be included in summaries if the prior 3 consecutive CZP doses are present.
- If a study participant is on a Q2W CZP dosing interval, and the study participant's CZP plasma concentration sample is taken <9 days or >19 days from the last CZP dosing, then it is excluded.
- If a study participant is on a Q4W CZP dosing interval, and the study participant's CZP plasma concentration sample is taken <23 days or >33 days from the last CZP dosing, then it is excluded,
- For the Week 1 CZP plasma concentration sample, if a study participant's sample is taken (too soon) <4 days after or (too late) >10 days after the Week 0 CZP dose, it is excluded, or
- For the Week 17 CZP plasma concentration sample, if a study participant's sample is taken (too soon) <4 days after or (too late) >10 days after the Week 16 CZP dose, it is excluded.

In addition, CZP plasma concentrations that have been analyzed outside the stability

Ine efficacy variables will be summarized using the Full Analysis Set (FAS). All safety and immunogenicity analyses will be based on the Safety Set (SS). Plasma concentration data will be summarized using the Pharmacokinetic Per-Protocol Set (PK-PP).

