### 8.1 **CZP** plasma concentrations

Only CZP plasma results analyzed using the ECLIA method will be summarized using the participants in the PK-PP set. CZP plasma concentrations are measured at Baseline, Weeks 1, 4, 12, 16, 17, 24, 32, 40, 48, every 24 weeks thereafter, the Early Discontinuation/EOT Visit, and the Final Visit; for study participants enrolled prior to Protocol Amendment 8, samples were not collected after implementation of Protocol Amendment 8. CZP plasma concentrations will be summarized by CZP dose (Original CZP Dose, Reduced CZP Dose) using geometric means, 95% CIs for the geometric mean, geometric CV, and the median, minimum and maximum concentrations.

The geometric CV will be calculated using the following formula:

$$geoCV(\%) = \sqrt{\exp(SD^2) - 1} * 100$$

where SD=standard deviation from the log-transformed data.

For the two CZP Dose groups, summaries at all available visits and plots of plasma concentration results will be produced separately by Baseline weight group, Baseline age group, ADAb participant status classification, ADAb titer classification (see Section 8.2) and, concomitant MTX use in combination with Baseline weight group.

Line-plots will be produced to summarize geometric mean (+/- 95% CI) plasma concentration over time. On each plot there will be separate plot lines for each subgroup category as described above. Plasma concentration will be plotted on both linear and semi-logarithmic scales.

In addition, spaghetti plots of CZP plasma concentrations over time will be produced for individual study participants, separately for each CZP dose group. Plots will be provided by Baseline age group, Baseline weight group, concomitant MTX use in combination with Baseline weight group. In each plot, different symbols/colors will be used to identify subgroup categories.

Concentrations below the limit of quantification of 320.0 ng/mL (0.32µg/mL) (BLQ) will be replaced by the LLOO divided by 2 for the calculation of descriptive statistics. The geometric

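### Read literally, the Q2W and Q4W sampling windows in SAP 3.5.1.1 exclude the nominal day-7 Week 1 and Week 17 samples that the visit-specific windows accept, and no precedence is stated

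*SAP*

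**What the plan says.** SAP Section 3.5.1.1 introduces its list with "The PK sample results taken at a specific visit will be excluded from analysis for the following reasons". Four of the bullets concern sampling time:

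- Q2W dosing: "sample is taken <9 days or >19 days from the last CZP dosing, then it is excluded".
- Q4W dosing: "sample is taken <23 days or >33 days from the last CZP dosing, then it is excluded".
- Week 1 sample: "<4 days after or (too late) >10 days after the Week 0 CZP dose, it is excluded, or".
- Week 17 sample: "<4 days after or (too late) >10 days after the Week 16 CZP dose, it is excluded".

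The last two bullets are linked by 'or'. No order of precedence is given, and neither general window mentions Week 1 or Week 17.

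Section 8.1 gives the schedule: "CZP plasma concentrations are measured at Baseline, Weeks 1, 4, 12, 16, 17, 24, 32, 40, 48", then every 24 weeks, with further samples at early discontinuation or end of treatment and at the Final Visit. Section 3.5 limits the timing exclusions to tables and figures that show geometric means; plots of individual data keep the samples. Section 5.2 has participants with at least one exclusion at a scheduled visit summarized and listed.

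**The concern.** If each bullet is a sufficient reason on its own, the visit-specific bullets can only add exclusions; they cannot rescue a sample that a general window has removed. Week 1 and Week 17 are due 7 days after a dose, below both the 9-day and the 23-day limit.

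Three things would follow from coding the text as written:

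- The Week 1 and Week 17 geometric means, confidence intervals and line-plot points would rest on samples drawn 2 to 3 days after the nominal day, or on nothing. Section 8.1 requires at least 3 values for summary statistics and 5 for the confidence interval.
- The Section 5.2 summary would count nearly everyone with a punctual Week 1 or Week 17 sample as having a PK exclusion, and so would say little about compliance.
- Two programmers could set different flags from the same text.

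**Working it through.** The plan states no figure to reproduce. The check sets each scheduled sample against the dosing calendar and applies each bullet separately.

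**Inputs**

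- Loading at Weeks 0, 2 and 4, Q2W in every weight group (Table 2–3).
- Maintenance Q2W from Week 6, except Reduced CZP Dose 10 to <20kg, which is Q4W from Week 8 (Table 2–3 and its footnote). Dose weeks are then 0, 2, 4, 6, 8, … on Q2W and 0, 2, 4, 8, 12, 16, … in the Q4W group.
- Kept by the general windows: days 9–19 (Q2W) and days 23–33 (Q4W). Kept by the Week 1 and Week 17 bullets: days 4–10.
- Visit window of ±3 days (Section 3.2.1).
- Assumption: at weeks that are also dosing weeks, the sample precedes that day's dose. The 9–19 and 23–33 day windows make sense only on that basis.

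**Formula:** days since last dose = 7 × (sample week − week of the preceding dose).

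| Sample | Interval | Days since last dose | General window | Visit-specific window |
|---|---|---|---|---|
| Week 1 | Q2W, all groups (loading) | 7 × (1 − 0) = 7 | excluded, 7 < 9 | accepted |
| Week 17 | Q2W | 7 × (17 − 16) = 7 | excluded, 7 < 9 | accepted |
| Week 17 | Q4W | 7 × (17 − 16) = 7 | excluded, 7 < 23 | accepted |
| Week 4 | Q2W, all groups (loading) | 7 × (4 − 2) = 14 | kept | none |
| Weeks 12, 16, 24, 32, 40, 48 | Q2W | 7 × 2 = 14 | kept | none |
| Weeks 12, 16, 24, 32, 40, 48 | Q4W | 7 × 4 = 28 | kept | none |

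The conflict arises at 2 of the 9 scheduled post-Baseline PK visits through Week 48. Early-discontinuation, end-of-treatment and Final Visit samples have no fixed place on this calendar and are left out of the count.

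**Days that pass both rules at Weeks 1 and 17**

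- Q2W: {4, …, 10} ∩ {9, …, 19} = {9, 10}. Five of the seven accepted days (4–8) are lost, including the nominal day 7.
- Q4W, Week 17: {4, …, 10} ∩ {23, …, 33} = ∅. All seven are lost.

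**With Weeks 1 and 17 exempt from the general windows:** days 4–10 are kept at both visits, and every other row of the table is unchanged.

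**The case against.** The best counter-argument is that nobody would read the list this way. Section 3.5 gives the aim as removing samples not taken when they should have been, and a day-7 sample at Week 1 was taken exactly when it should have been. The visit-specific bullets define too soon and too late for these two visits. On the literal reading their 4-day limit does no work, because anything under 4 days is already under 9 or 23, and at Week 17 on Q4W the bullet would have nothing left to decide. A reading that empties explicit rules is the less plausible one. This stands: the intent was almost certainly to judge Weeks 1 and 17 by days 4–10 alone.

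It does not dispose of the point. The first two bullets of the same list carry explicit sub-bullets saying when a result is put back into the summaries; the interval bullets carry none. Intent has to be inferred against the wording.

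A reader might infer more than the text supports:

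- *That every on-schedule Week 1 and Week 17 sample is removed.* On Q2W, days 9 and 10 survive, and they lie inside both the ±3-day visit window and the 4–10 day rule. They are late, not off schedule. Total loss applies only at Week 17 in the Q4W group.
- *That the summaries already produced are empty.* These windows also stand in the changes logged for SAP Amendments 4 and 5, and the Updated Week 24 Interim Analysis is complete. The SAP neither shows how the flag was programmed nor reports a gap at these visits.
- *That the main PK conclusions are at risk.* The primary concentration variables are at Weeks 16 and 48 (Section 2.2.1.1), and the comparison with study RA0138 used Weeks 12 and 24 (Section 12.1). All four are sampled 14 or 28 days after a dose and are kept. Weeks 1 and 17 are other time points, and no hypothesis is tested.

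**Conclusion.** The point holds as an internal contradiction in a written rule. Followed to the letter, Section 3.5.1.1 excludes the nominal day-7 sample at Week 1 in all groups and at Week 17 on either dosing interval, although the bullet written for that visit accepts it. Two of seven accepted days survive on Q2W and none at Week 17 on Q4W.

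The reach is modest: geometric-mean tables and line plots at two non-primary visits, and the Section 5.2 exclusion summary. Spaghetti and individual plots, listings, Weeks 16 and 48, and the Week 12 and 24 adult comparison are untouched.

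The conclusion rests on each bullet being a sufficient reason for exclusion, as the list is worded, and on samples at dosing weeks being drawn before the dose. Whether any output is actually affected depends on the flag program, which the SAP does not show. The text should still be corrected, because the final analysis is to follow this amendment.

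**What to change.** Add to both the Q2W and the Q4W bullet in Section 3.5.1.1: *except Week 1 and Week 17 samples, to which only the 4–10 day rules below apply*. Make clear that 'only' refers to the timing windows, so that the missed-dose and assay-stability exclusions still cover these samples.

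Then check the exclusion-flag program against the amended text. A day-7 sample at Week 1 and at Week 17 should be retained on Q2W, and at Week 17 on Q4W. If the program already does this, nothing changes but the wording. If not, rerun the Week 1 and Week 17 geometric-mean outputs and the Section 5.2 exclusion summary. The cost is one clause and one program check; no other scheduled sample changes status.
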